5.4.3. Compliance and withdrawal of Study Participants

Study participants are free to withdraw from the trial at any time. Reasons, if given, will be recorded and data collected up to that time point may be used in the final analyses, unless the patient specifically requests that their data are not used. If the patient withdraws consent to have their data stored, then this will be documented on the trial CONSORT flow diagram as 'withdrawn' and their data will not be used in the final analyses. Patients may withdraw from participation in active follow up but data will continue to be collected unless the patient requests otherwise. The patient may be willing to give a reason for withdrawal, but this is not obligatory.

Crossover

Any patient in the control group that has a CTCA as part of routine care within 30 days of randomisation will be defined as a crossover and does not need to be recorded as a deviation.

Non-adherence

This will be defined as to have occurred in any participant not receiving a reported CTCA if randomised to it within 72 hours of the randomisation and this would be recorded as a deviation. This allows ambulatory CTCA to be delivered when appropriate.

Individual site retention, crossover and non-adherence will be monitored and reviewed at the Project Management Group and Trial Steering Committees meetings.

6. STUDY ASSESSMENTS

Patients will be screened, consented, recruited and randomised in the ED, Cardiology or MAU of participating centres within 24 hours of arrival to the hospital. All patients will receive standard acute clinical assessment including a presentation 12-lead ECG and troponin measurement.

CTCA will be delivered and reported by a trained radiologist or cardiologist within an established radiology service as soon as possible, ideally within 2 hours of procedure and reported and communicated immediately to the treating clinician.

Patients randomised to standard care will receive the standard management for patients with suspected or confirmed ACS at that NHS hospital site. The only difference will be the early use of CTCA in the intervention arm and the subsequent impact on patient care after the result is provided to the clinician for clinical decision making. Local chest pain management guidelines will be collected, or confirmation obtained from PI that CTCA is not currently in routine use for eligible patients (including change in practice, during the period of the trial).

CTCA delivery

The technology being assessed is 64 slice or greater multidetector CT scanners enabled to perform ECG-gated cardiac studies. The examination may include a non-contrast ECG-triggered acquisition for calcium scoring (if part of local protocol) and a post-contrast ECG-gated acquisition covering the whole of the heart and the root of the aorta.

Patients must be able to hold their breath for >20 seconds. The intervention will be for no longer than 30 minutes and the patient will be observed for a period of 30 minutes afterwards.

Radiation reduction techniques will be employed and, where appropriate, intravenous or oral beta blockade (or alternative heart rate limiting agent) will be used to reduce heart rate (target of <70 /min) enabling significant radiation dose saving protocols.

Due to the variation in conversion factors used by sites to convert dose-length product (DLP) to effective dose in mSv, radiation dose will be routinely reported for the trial as DLP. A DLP to mSv conversion factor of 0.014 mSv/mGy/cm will be used for trial reporting in line with recent publications in this area of research.

A typical participant with a heart rate below 70 beats per minute in sinus rhythm and a BMI <25 should have a DLP ≤ 686 mGy.cm and cases exceeding this will be considered to be a protocol deviation. Deviations will be reviewed by a Radiologist/Cardiologist in the central trials team and any cases which have an impact on patient safety or study outcomes will instead be reported as a protocol violation. For other participants, without the typical characteristics stated above, DLP values ≥686 mGy.cm are anticipated as part of routine clinical practice (for example, due to the need for continuous retrospectively gated scanning in some participants with arrhythmia). For such participants, any DLP which exceeds 1500 mGy.cm will be considered to be a protocol deviation. Deviations will be reviewed by a Radiologist/Cardiologist in the central trials team and any cases which have an impact on patient safety or study outcomes will instead be reported as a protocol violation.

All participating centres will be required to verify that their CTCA imaging protocol complies with the doses outlined in the research protocol prior to recruitment and patient doses will be recorded and monitored as part of the study. Iodine based contrast agent will be administered intravenously using the standard local procedure at each site. The use of GTN for coronary artery dilatation will be used at the discretion of individual centres.

Further guidance can be found in the trial CT coronary angiography guidance document.

CTCA result reporting

CTCA will be usually reported by a trained radiologist or cardiologist at recruiting centres as soon as possible, ideally within 2 hours and communicated immediately to the treating clinician.

The clinical report detailing the results should be reported according to the Society of Cardiovascular CT guidelines, with the use of the AHA coronary artery segment model and will include both the calcium score if calculated and the presence of cardiac and non-cardiac findings. Stenoses will be quantified as: no significant coronary artery disease (estimated stenosis <10%), mild non-obstructive disease (estimated stenosis of 10-49%), moderate non-obstructive disease (estimated stenosis of 50-70%), or obstructive coronary artery disease (estimated stenosis of >70%).

The research Scan Report should also be completed by the radiologist/cardiothoracic and will record scanner technology, acquisition protocol, dose length product and patient characteristics.

A proportion of CTCA reporting may be delivered remotely using remote access technology by a core group of readers. Transfer of image data is simple and a well-established process within the UK for out-of-hours reporting. Secure electronic transfer via the national PACS system (with required permissions) will allow reporting using voice recognition dictation either direct to the host radiology information system or via e-mail direct to the referring centre.

QA reporting of CTCA scans

A proportion of scans will be re-reported by experts independent to the trial site and blinded to the initial report to measure inter-observer reliability. The first 10 scans carried out at each site will undergo this process, as detailed in the working practice document 'Dual Quality Assurance Reporting of CTCA Scans'.

CTCA for future research

The scans sent for QA reporting will be retained for future research. Additional scans will be collected from sites willing to provide these for this research repository.

Impact of technology on care pathway

A trial guideline on the management of trial participants depending on CTCA result is listed in appendix 1. This will, however, not be mandated as this is a pragmatic trial investigating the impact of the diagnostic intervention on practice and clinical outcomes.

Current alternative investigation strategies and standard care arm

Investigation guidelines and strategies for each centre will be collected and the use of CTCA will be monitored during the trial. Each centre will be requested not to use CTCA in the routine assessment of suspected or confirmed ACS during trial recruitment and should inform the trials team about any changes to local practice.

7. DATA COLLECTION

Data collection for primary, secondary and safety clinical outcomes

Data will be collected by the research team from routinely available NHS hospital records or trial specific documentation and will include the following categories: eligibility criteria, consent and baseline demographics, comorbidities, regular treatment, ECG results, vital signs, blood results, admission and discharge diagnoses, cardiology and other relevant investigations or interventions, length of stay, repeat hospitalisations and adverse events. Detail will also be collected on the trial intervention including timing, details of the procedure including dose, reporting clinician, report including incidental findings, and any adverse events as a result of the intervention.

Collection of cost and health outcome data

Length of stay and major adverse cardiac events will be recorded from telephone contact of patients, hospital and primary care records, and deaths from the Central Registry Office or equivalent. At baseline, 1, 6 and 12 months, quality of life and angina symptoms will be measured using the EQ-5D-5L and ROSE questionnaires by direct patient interview, postal or email survey with telephone follow up for non-responders after two mailings two weeks apart.

8. STATISTICS AND DATA ANALYSIS

Statistical Analysis

The trial will be reported on an intention-to-treat basis. The primary outcome is defined as first event of all cause death or subsequent non-fatal MI type 1 or 4b. Time to primary outcome is defined as time from randomisation to primary outcome. Patients discontinuing the study (for any reason) prior to reaching primary outcome will have their time to primary outcome censored at the last contact date. The relationship between intervention and the primary outcome will be analysed using Cox proportional hazard regression adjusted for study site (used to stratify the randomisation), baseline GRACE score, and previous CAD. The results will be expressed as a hazard ratio with the corresponding 95% confidence intervals and p-value. The individual elements of the composite primary outcome will be reported separately. Subgroup analysis on the primary outcome is planned for age, sex, baseline GRACE score, previous CAD, baseline ECG result, baseline troponin concentration, and presentation to a study site with or without on-site invasive coronary angiography facilities. These will be assessed by examining the effect of entering the treatment by subgroup interaction into the Cox regression model. Secondary outcomes will be analysed using appropriate methods: logistic regression for binary outcomes and linear regression for normally distributed continuous outcomes, adjusted as described above. Continuous outcomes that are not normally distributed will be analysed using appropriate nonparametric techniques. Every effort will be made to minimise missing data, and our primary analysis will be a complete case analysis. If there is a sufficient level of missing data for it to affect our conclusions, a multiple imputation analysis will be undertaken, using clinically appropriate variables, as a sensitivity analysis. Significance testing will use a hierarchical approach – for the primary outcome and the key secondary outcomes, statistical significance will be declared if the outcome in question, and all prior outcomes listed, have $p < 0.05$. P-values will be reported for all other outcomes but will not be declared to be significant.

A full statistical analysis plan will be written during the trial and finalised prior to database lock.

Economic analysis

Economic evaluation will assist policy makers to decide whether multidetector computed tomography scanning represents a cost-effective use of NHS resources. Cost-effectiveness analysis will be used to estimate the incremental costs and quality adjusted life years (QALYs). The economic analysis will include a) within-trial cost effectiveness analysis (i.e. comparing the observed costs and QALYs of the

intervention and control groups during the trial period), and b) analysis of the long-term cost effectiveness of CTCA, by adapting an existing decision analytic model [Goodacre S et al, 2013; Thokala P et al, 2012],

In the within trial cost-effectiveness analysis, incremental cost per QALY gained by using CTCA compared to standard care will be estimated by calculating the area under the curve for health utility using the EQ-5D-5L and health service costs up to one year. Quality of life will be measured using the EQ-5D-5L at baseline and 1, 6 and 12 months after index admission. All health care consumption and costs will be estimated from a health care perspective using patient self-reported questionnaires, and from hospital records. Costs will be attributed to the need for (i) continued hospitalisation, (ii) additional invasive or non-invasive imaging, (iii) drug therapy, and (iv) rehospitalisation for myocardial ischaemia. Resource use will be measured for each patient in the trial and multiplied by national average costs to provide the estimated cost per patient.

Long term cost-effectiveness will be estimated by adapting an existing model, developed for as part of a previous HTA evidence synthesis project [Goodacre S et al, 2013; Thokala P et al, 2012]. The model used published sources to capture the life expectancy, annual costs and corresponding annual utilities, based on whether they had MI at initial hospital attendance and whether they suffered reinfarction. The data from the trial will be input into the model which estimates the lifetime QALYs and costs of surviving patients. The results will be reported as the incremental cost effectiveness ratio (ICER) of CTCA arm compared to usual care.

Sensitivity analyses will explore the potential impact of parameters upon costs, QALYs and ICERs. Parameter uncertainty will be included in probabilistic sensitivity analysis based on Monte Carlo simulation. Cost effectiveness acceptability curves (CEACs) will be plotted to identify the probability of the CTCA arm being cost effective compared to standard care for a range of threshold values for an additional QALY.

9. ADVERSE EVENTS

The Investigator is responsible for the detection and documentation of events meeting the criteria and definitions detailed below.

All adverse events (AE) meeting the criteria outlined in section 9.2.1 must be reported in detail on the Adverse Events CRF. Participants undergoing CTCA will be instructed to contact their Investigator after consenting to join the trial if any symptoms develop from consent until 10 days after joining the study. Participants in the standard care arm that go on to receive a scan should also have any relevant AEs recorded.

In the case of an AE, the Investigator should initiate the appropriate management according to their medical judgment. Participants with AEs present at the last visit must be followed up until resolution of the event.

9.1. DEFINITIONS

Adverse Event (AE)

Any untoward medical occurrence in a study participant, which does not necessarily have a causal relationship with the study intervention.

Adverse Reaction (AR)

Any untoward and unintended response that has occurred due to the intervention.

Serious Adverse Event (SAE) or Serious Adverse Reaction (SAR)

Any AE or AR that:

- results in death of the study participant
- is life-threatening*
- requires inpatient hospitalisation[^] or prolongation of existing inpatient hospitalisation

- results in persistent or significant disability or incapacity
- consists of a congenital anomaly or birth defect
- results in any other significant medical event not meeting the criteria above

* Life-threatening in the definition of an SAE or SAR refers to an event where the participant was at risk of death at the time of the event. It does not refer to an event which hypothetically might have caused death if it were more severe.

^ Any hospitalisation that was planned prior to randomisation will not meet SAE criteria. Any hospitalisation that is planned post randomisation, will meet the SAE criteria.

9.2. IDENTIFYING AEs AND SAEs

All AEs and SAEs that meet the reporting criteria in sections 9.2.1 and 9.2.2 will be recorded from the time a participant signs the consent form to take part in the study until 10 days afterwards. Patients who have consented to the trial will be asked to contact the research team if they experience any untoward effects within these 10 days.

AEs and SAEs may also be identified via information from support departments e.g. laboratories or the patient record. These will be reported to the investigator within 7 days of identification.

Any AEs or SAEs out-with the given definitions will not be recorded during the study.

9.2.1 Adverse Events relating to CT Scanning

The following Adverse Events can be attributed to the application of CTCA and should be recorded as an AE (and reported as an SAE if appropriate):

- Contrast related anaphylaxis/allergy requiring treatment, requiring critical care admission or resulting in cardiac arrest or death.
- Contrast related AKI or Acute on CKD
- Side effects or complications related to beta blocker (or alternative HR-limiting medication) or Glyceryl Trinitrate premedication.

No other AEs out-with this definition will be recorded on the CRF.

9.2.2 SAE reporting and exemptions

All SAEs that meet the definition given in section 9.1 should be reported to the Sponsor unless they meet the exemption criteria below. SAEs should be reported from consent until 10 days afterwards.

These events are anticipated to occur in this patient group and will not be reported to the Sponsor but will be collected in the CRF for all participants:

- Malignant arrhythmia – CHB requiring pace maker; VT/VF/SVT requiring cardioversion or defibrillation
- Cardiac Arrest
- Death
- ICU admission
- Procedure related MI, coronary artery dissection, pseudo aneurysm

9.3. RECORDING AEs AND SAEs.

When an AE/SAE occurs, it is the responsibility of the Investigator to review all documentation (e.g. hospital notes, laboratory and diagnostic reports) related to the event. The Investigator will then record all relevant information in the CRF and on the SAE form (if the AE meets the criteria of serious).

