9.4.1. Assessment of Causality

The Investigator will make an assessment of whether the AE is likely to be related to the study intervention according to the following definitions:

Unrelated: where an event is not considered to have occurred as a result of the study intervention.

Possibly Related: The nature of the event, the underlying medical condition, concomitant medication or temporal relationship make it possible that the AE has a causal relationship to the study intervention.

Where there are two assessments of causality (e.g. between PI and CI), the causality assessment by the Investigator cannot be downgraded. In the case of a difference of opinion, both assessments are recorded and the 'worst case' assessment is used for reporting purposes.

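### Protocol 9.2.2 exempts listed serious events from sponsor reporting with no causality condition, in conflict with 9.2.1 and 9.5, and nothing says which section prevails

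*Protocol*

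**What the plan says.** Protocol 9.2.2 sets a general rule with an exception. Events meeting the seriousness definition in 9.1 "should be reported to the Sponsor unless they meet the exemption criteria below", over a window of 10 days from consent. The exception covers malignant arrhythmia, cardiac arrest, death, ICU admission, and procedure-related MI, coronary dissection or pseudoaneurysm. The reason given is "These events are anticipated to occur in this patient group", and the consequence is that they "will not be reported to the Sponsor but will be collected in the CRF for all participants".

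Protocol 9.2.1 lists events that can be attributed to CTCA. One is "Contrast related anaphylaxis/allergy requiring treatment, requiring critical care admission or resulting in cardiac arrest or death". The others are contrast-related kidney injury and complications of heart-rate-limiting or nitrate premedication. Each "should be recorded as an AE (and reported as an SAE if appropriate").

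Protocol 9.4 asks for a causality assessment of every adverse event. Section 9.4.1 offers two categories: Unrelated, "where an event is not considered to have occurred as a result of the study intervention", and Possibly Related, where for example "concomitant medication or temporal relationship make it possible that the AE has a causal relationship to the study intervention". If two assessors differ, the worst-case "assessment is used for reporting purposes".

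Protocol 9.3 calls for an SAE form whenever an event is serious. Section 9.5 requires the investigator to inform the ACCORD office, which 10.1 says provides sponsorship, within 24 hours at the latest. Neither section refers to the exemption.

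**The concern.** An exemption for events that the underlying disease is expected to produce is a sensible way to limit reporting in an acute cardiac population. The reason for it weakens once a listed event may have been caused by the trial intervention. The protocol has the means to separate the two cases, in 9.4.1, but 9.2.2 does not use it. The gravest possible harms of the scan, the contrast or the premedication would appear as the same kinds of event that 9.2.2 exempts.

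What is at stake is how soon the sponsor learns of such an event. A site that reads 9.2.2 literally records it in the CRF and sends nothing. A site that reads 9.2.1 or 9.5 literally reports it within 24 hours. Two sites can handle the same event differently, and each can cite the protocol.

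**Working it through.** The plan gives no figure to reproduce and no arithmetic applies, so the check sets the sections side by side.

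**Step 1: is there a causality condition in 9.2.2?** No. Cardiac arrest, death and ICU admission stand without any qualifier. The arrhythmia item is qualified by the treatment needed, and the last item by its link to a procedure. None refers to 9.4.1.

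**Step 2: does the stated reason supply one?** Not in words. The reason concerns the patient group. Section 9.4.2 judges expectedness against the study intervention, which is a different yardstick. One item is defined by its link to a procedure (which procedure is not stated), so the list is not plainly confined to the natural course of the disease.

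**Step 3: apply each section to three cases.**

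| Listed event, judged possibly related | 9.2.1 | 9.2.2 | 9.3 and 9.5 |
|---|---|---|---|
| Contrast anaphylaxis leading to arrest, death or critical care (when that is ICU) | Report as SAE, if appropriate | Exempt on a literal reading | SAE form; report within 24 hours |
| Heart block needing a pacemaker, judged a complication of heart-rate-limiting premedication | Report as SAE, if appropriate | Exempt on a literal reading | SAE form; report within 24 hours |
| Death, arrest or ICU admission judged possibly related, but outside the 9.2.1 list | Silent | Exempt | SAE form; report within 24 hours |

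In the first two rows the sections contradict each other. The proviso in 9.2.1 does not settle the matter: it may mean *if the event is serious*, or it may defer to 9.2.2. In the third row 9.2.1 gives no help. Section 9.3 asks for the form, but only the general sentence in 9.5 points to sending it.

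**Step 4: is there a rule of precedence?** None was found in sections 9 to 9.6. The worst-case rule in 9.4.1 says that causality matters for reporting, but 9.2.2 makes no use of the result.

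**Step 5: what is not affected?** Listed events are collected in the CRF for all participants. Death from any cause is part of the primary endpoint and is followed for a year. SAP 4.7 tabulates adverse events by relatedness. That table belongs to the analysis and is no substitute for a prompt report.

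**The case against.** The strongest reply is that the sections can be read in harmony. Section 9.2.1 sorts events by attribution to CTCA, and 9.2.2 by what the patient group is expected to suffer. On that reading, the event in a contrast death is the anaphylaxis, which is not on the 9.2.2 list, and the exemption never reaches it. Sections 9.3 and 9.5, being unqualified, support this.

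Much of that stands. It rules out a stronger claim that a reader might infer, namely that the protocol plainly waives reporting of contrast or premedication harms. It does not: for those events the sections conflict. The reply does not remove the problem, because the text never says that the list is limited to disease-course events, and the third case in the table lies outside 9.2.1 altogether.

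A second tempting inference is that related deaths would go undetected or drop out of the analysis. The CRF collection, the endpoint definition and the SAP table all contradict that.

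A third is to treat the overlap between the two lists as a measure of the problem's size. It is not. It shows where the wording collides and says nothing about how often such events occur.

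**Conclusion.** The point holds as a missing condition and an unresolved conflict. The 9.2.2 exemption takes no account of causality, 9.2.1 and 9.5 point the other way, and no section settles the matter. A site could follow 9.2.2 and not promptly notify the sponsor of a listed event judged possibly related to the scan, contrast or premedication.

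The absence of the condition is certain from the text. That a site would act on the literal reading is a possibility, not something the documents show. The effect is confined to prompt sponsor notice within the 10-day window. The documents give no rate for serious scan-related events, so no expected count can be derived. The primary analysis is not affected. The point is worth fixing because the remedy is cheap and concerns the most serious potential harms of the intervention.

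**What to change.** Reconcile the three sections in one amendment, with a memo to sites.

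- **In 9.2.2**, add: *A listed event is exempt only if it has been assessed as Unrelated under 9.4.1. A listed event assessed as Possibly Related, and any serious event meeting 9.2.1, is reported under 9.5.*
- **In 9.5**, add: *except events exempt under 9.2.2*.
- **Clerical, in the same amendment:** 9.5 cites the wrong subsections. Causality is 9.4.1 and expectedness is 9.4.2.

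The cost is more SAE reports to send and follow up. Possibly Related is broad, since timing alone may be enough, and the trial is open, so the added number may not be small; the documents do not allow an estimate. Section 9.3 already asks for an SAE form for each serious event, so the extra work should be mainly in transmission. Sites would also have to judge causality for listed events soon enough to meet the 24-hour limit.

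The amendment may come too late. The SAP, finalised on 19 August 2020, says that the five largest sites had each randomised more than 100 patients, which suggests, but does not prove, that recruitment was well advanced. If recruitment and the 10-day window have closed, send the sponsor one listing of the exempt events with their causality assessments instead. That depends on causality having been recorded for them. Section 9.4 asks for the assessment, but the documents do not show a CRF field that holds it for exempt events, so check this first.
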